**Table 3-2 Study VX16-809-121: Treatment Period and Safety Follow-up Visit**

Event/Assessment a	Treatment Period									ETT Visit b	Safety Follow-up Visit c
	Part 1: Placebo-controlled Period				Part 1/ Part 2 d	Part 2: Open-label Period e					
	Day 1	Day 3 (± 1 Day)	Day 15 (± 3 Days)	Weeks 12, 24, 36 (± 7 Days)	Week 48 (± 7 Days)	Day 338 f (± 1 Day)	Day 350 (± 3 Days)	Weeks 60, 72, 84 (± 7 Days)	Week 96 (± 7 Days)		
Clinic visit	X		X	X	X		X	X	X	X	X
Telephone contact g		X				X					
Randomization h	X										
Stature and weight i	X		X	X	X		X	X	X	X	X
Vital signs j	X k		X	X	X k		X	X	X	X	X
OE l					X m				X m,n	X m,n	X m,n
Full PE o	X			Week 24	X			Week 72	X	X	X

- a Assessments will be performed before study drug dosing unless noted otherwise (Section 11.1).
- b If the ETT Visit occurs 10 days or later after the last dose of study drug, the Safety Follow-up Visit will not be required. Subjects who prematurely discontinue study drug treatment for AEs should be followed until the AE is considered resolved.
- c The Safety Follow-up Visit is required for 1) subjects who complete their ETT Visit <10 days after the last dose of study drug and 2) subjects who interrupt study drug treatment and complete their Week 96 Visit <10 days after the last dose of study drug; it is not required for subjects who continue onto commercially available, physician-prescribed LUM/IVA within 2 weeks (± 4 days) of completing study drug treatment at the Week 96 or ETT Visit.
- d The first open-label dose of LUM/IVA will be the dose administered at the Week 48 Visit after completion of the predose assessments.
- e If the subject's Week 48 Visit is delayed, all subsequent visits must be delayed accordingly based on the actual Week 48 Visit date.
- f The Day 338 Visit (telephone contact) should occur 1 to 3 days after the actual date of the Week 48 Visit, regardless of whether it is Study Day 338.
- g Telephone contacts will be made to assess the subject's status, any AEs, medications, treatments, and procedures.
- h Randomization must only occur after all inclusion and exclusion criteria are met and before the first dose of study drug. Randomization will be done through IWRS and may occur on Day -1.

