8.2 Part 1 Treatment-Emergent Period

The **Part 1 Treatment-Emergent (TE) Period** will include the time from the first dose of study drug (including the matched placebo) until 14 days after the last dose of study drug of Part 1 or the completion of study participation of Part 1, whichever occurs first.

Completion of study participation of Part 1 is defined as the following:

- For subjects who complete Part 1 and enter Part 2: the day prior to the first dose of study drug of Part 2
- For subjects who prematurely discontinue study drug treatment during the Part 1 treatment period but do not withdraw consent (and assent, as applicable): the latest of the Week 48 Visit, ETT or Safety Follow-up Visit (if required)
- For subjects who withdraw consent or assent: date of withdrawal of consent or assent, whichever is earlier.

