8.4 Part 2 Safety Period

The **Part 2 Safety Period** will include the time from the first dose of study drug of Part 2 until 14 days after the last dose of LUM/IVA or the completion of study participation, whichever occurs first.

Completion of study participation is defined as:

- For subjects who complete the study, the latest of the ETT Visit or Safety Follow-up Visit (if required).
- For subjects who prematurely discontinue study drug treatment during the study but do not withdraw consent (and assent, as applicable): the latest of ETT or Safety Follow-up Visit (if required).
- For subjects who withdraw consent or assent: date of withdrawal of consent or assent, whichever is earlier.

The Part 2 Safety Period will be used for analysis of safety data in the FA.

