9.2.3 Safety Analysis

Unless otherwise specified, all safety analyses of Part 1 analysis will be based on data from the Part 1 TE period for all subjects in the Safety Set. Subjects will be analyzed according to the treatment they actually received in the study Part 1. For subjects who have received study drug from more than one treatment, i.e. received both LUM/IVA and Placebo study drug, the treatment group allocation will be the LUM/IVA.

The overall safety profile of study drug will be assessed in terms of the following safety and tolerability assessments:

- Treatment-emergent adverse events (TEAEs)
- Clinical laboratory values
- Vital signs
- Ophthalmologic examinations (OEs)
- Physical examinations (PEs)

Only descriptive analysis will be performed for safety, and no confidence interval will be computed.

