9.2.3.2 Clinical Laboratory

For the treatment-emergent laboratory assessments during the Part 1 TE period, the observed values and change from study baseline of the continuous hematology and chemistry results will be summarized in SI units at each visit by treatment group.

The number and percentage of subjects meeting at least 1 threshold analysis criterion during the Part 1 TE period will be summarized by treatment group. The threshold analysis criteria are provided in [Appendix D](#).

In addition, a listing containing individual subject hematology and chemistry values during the Part 1 TE period will be provided with a column indicating outside reference range or not. This listing will include data from both scheduled and unscheduled visits.

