9.2.3.4 Ophthalmologic Examination

The OE results during Part 1 TE period will be presented in individual subject data listings.

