12 LIST OF APPENDICES

Appendix A: Analysis Visit Windows for Safety and Efficacy Assessment

[figure not shown]
Table 12-1 Analysis Visit Windows for Safety and Efficacy Assessments

Assessment	Visit ¹	Target Study Day	Analysis Visit Window ^{2,3,4,5} (in study Part 1 or 2 days)
Safety Assessment			
Serum Chemistry	Day 1 (Study Baseline) Day 15 Week 12 Week 24 Week 36 Week 48	1 15 85 169 253 337	≤1 Pre-dose [1, 49] [50, 126] [127, 210] [211, 294] [295, min(337+67, 1 st dose of Part 2)]
	Day 350 Week 60 Week 72 Week 84 Week 96 Safety Follow-up	Part 2 Day 15 Part 2 Day 85 Part 2 Day 169 Part 2 Day 253 Part 2 Day 337 N/A	[1 st dose of Part 2, 49] [50, 126] [127, 210] [211, 294] [295, 337+67] Use nominal visit
Hematology	Day 1 (Study Baseline) Week 12 Week 24 Week 36 Week 48	1 85 169 253 337	≤1 Pre-dose [1, 126] [127, 210] [211, 294] [295, min(337+67, 1 st dose of Part 2)]
	Week 60 Week 72 Week 84 Week 96 Safety Follow-up	Part 2 Day 85 Part 2 Day 169 Part 2 Day 253 Part 2 Day 337 N/A	[1 st dose of Part 2, 126] [127, 210] [211, 294] [295, 337+67] Use nominal visit
Vital signs (excluding Weight and Stature)	Day 1 (Study Baseline) Day 15 Week 12 Week 24 Week 36 Week 48	1 15 85 169 253 337	≤1 [1, 49] [50, 126] [127, 210] [211, 294] [295, min(337+67, 1 st dose of Part 2)]
	Day 350 Week 60 Week 72 Week 84 Week 96 Safety Follow-up	Part 2 Day 15 Part 2 Day 85 Part 2 Day 169 Part 2 Day 253 Part 2 Day 337 N/A	[1 st dose of Part 2, 49] [50, 126] [127, 210] [211, 294] [295, 337+67] Use nominal visit
Efficacy Assessment			

Table 12-1 Analysis Visit Windows for Safety and Efficacy Assessments

Assessment	Visit ¹	Target Study Day	Analysis Visit Window ^{2,3,4,5} (in study Part 1 or 2 days)
MRI	Day 1 (Study Baseline) Week 48	1 337	≤1 Pre-dose (1, min(337+67, 1 st dose of Part 2)]
	Week 96	Part 2 Day 337	[1 st dose of Part 2, 337+67]
MBW [REDACTED]	Day 1 (Study Baseline) Week 12 Week 24 Week 36 Week 48	1 85 169 253 337	≤1 Pre-dose (1, 126] [127, 210] [211, 294] [295, min(337+67, 1 st dose of Part 2)]
	Week 60 Week 72 Week 84 Week 96	Part 2 Day 85 Part 2 Day 169 Part 2 Day 253 Part 2 Day 337	[1 st dose of Part 2, 126] [127, 210] [211, 294] [295, 337+67]
Weight and Stature	Day 1 (Study Baseline) Day 15 Week 12 Week 24 Week 36 Week 48	1 15 85 169 253 337	≤1 Pre-dose [1, 49] [50, 126] [127, 210] [211, 294] [295, min(337+67, 1 st dose of Part 2)]

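### SAP 8.2 closes the Part 1 treatment-emergent period a day too early, so same-day pre-dose Week 48 safety results miss the Part 1 threshold counts and listings

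*SAP*

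**What the plan says.** SAP 8.2 ends the Part 1 TE period at the earlier of 14 days after the last Part 1 dose and completion of Part 1 participation. It defines the latter as "For subjects who complete Part 1 and enter Part 2: the day prior to the first dose of study drug of Part 2".

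Footnote d to protocol Table 3-2 places that dose on the visit day: "The first open-label dose of LUM/IVA will be the dose administered at the Week 48 Visit after completion of the predose assessments". Footnote a sets the default order: "Assessments will be performed before study drug dosing unless noted otherwise".

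The SAP then ties Part 1 safety to this period. Section 9.2.3 says that, unless otherwise specified, "all safety analyses of Part 1 analysis will be based on data from the Part 1 TE period for all subjects". Section 9.2.3.2 says "The number and percentage of subjects meeting at least 1 threshold analysis criterion during the Part 1 TE period will be summarized", and limits the laboratory listing in the same way. Section 9.2.3.3 does so for the vital-signs listing. Section 9.2.3.4 says "The OE results during Part 1 TE period will be presented in individual subject data listings".

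On the other side of the boundary, the Part 2 Safety Period (SAP 8.4) "will include the time from the first dose of study drug of Part 2".

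Appendix A draws a different line. Its Part 1 Week 48 window for chemistry, hematology and vital signs is "295, min(337+67, 1 st dose of Part 2". A note to the table keeps the Week 48 visit day in Part 1 until the first Part 2 dose. Note 3 treats a scheduled laboratory or vital-sign result on a first-dose day as pre-dose when its order relative to the dose is unknown.

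**The concern.** A pre-dose Week 48 result is the end-of-treatment measurement for Part 1. It normally carries the date of the first Part 2 dose, one day after SAP 8.2 has closed the Part 1 TE period. Under SAP 8.4 as worded it also comes before Part 2 opens, so it belongs to neither period.

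Part 1 is the only placebo-controlled safety comparison in the study. A liver-enzyme or other laboratory threshold crossing first seen at that draw would appear in neither the Part 1 nor the Part 2 threshold table. A same-day Week 48 OE would be left out of the Part 1 TE listing.

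If a programmer instead applies both periods by calendar date alone, the same results move into Part 2. They are then attributed to open-label LUM/IVA, even for children who had taken only placebo when the sample was drawn. That is wrong too.

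**Working it through.** The plan gives no figure to reproduce. The check is date logic on its stated rules.

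**Inputs**
- D = study day of the first Part 2 dose. The Week 48 target is Day 48 × 7 + 1 = 337, with a ±7-day visit window (330 to 344). The upper limit in Appendix A is 337 + 67 = 404.
- TE end (SAP 8.2) = min(last Part 1 dose + 14, D − 1).
- Week 48 window (Appendix A) = [295, min(404, D)], up to the first Part 2 dose.

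**Same-day pre-dose result (day D), last Part 1 dose on D − 1**

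| D | TE end | In TE period? | Week 48 window | In window? |
|---|---|---|---|---|
| 330 | min(343, 329) = 329 | No | [295, 330] | Yes |
| 337 | min(350, 336) = 336 | No | [295, 337] | Yes |
| 344 | min(357, 343) = 343 | No | [295, 344] | Yes |
| 404 | min(417, 403) = 403 | No | [295, 404] | Yes |

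The answer does not change if the last Part 1 dose falls on D itself. Protocol 9.6 allows this for an afternoon visit: morning dose at home, evening dose in clinic. The TE period then ends a day before the last Part 1 dose.

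Results from D − 1 or D − 7 are inside both periods. Bloods drawn with an early MRI, and an OE done up to 7 days early, are therefore kept. Table 3-2 gives no such early option for vital signs.

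**What one affected child loses from Part 1** (schedule from protocol Table 3-2)
- Chemistry at Day 15 and Weeks 12, 24, 36, 48: 1/5 = 20%.
- Hematology at Weeks 12, 24, 36, 48: 1/4 = 25%.
- Vital signs at Day 15 and Weeks 12, 24, 36, 48: the pre-dose set at 1 of 5 visits after Day 1 = 20%.
- OE: Week 48 is the only scheduled Part 1 examination after screening, apart from early termination.

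The last scheduled laboratory result retained is then Week 36 (target Day 253). The uncovered stretch is 337 − 253 = 84 days out of 337 − 1 = 336, and 84/336 = 25%. This is the missing Week 48 draw expressed as time, not a further loss.

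**Which outputs are affected.** Threshold counts and listings are defined by period, so the loss follows directly from the text. The by-visit laboratory and vital-sign summaries are ambiguous: Appendix A assigns the results to Week 48, but SAP 9.2.3.2 and 9.2.3.3 also confine those summaries to the TE period. Protocol 12.3.4.6 asks for safety by arm covering baseline through Week 48, which supports keeping the results in Part 1.

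**With the boundary moved** to the time of the first Part 2 dose, a pre-dose result on day D is inside the TE period in every case above.

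**The case against.** The strongest reply is that the SAP already shows its intent. Section 9.2.3 applies the TE restriction only where nothing else is specified, section 9.1 sends visit assignment to Appendix A, and Appendix A places pre-dose Week 48 in Part 1. The intent is indeed clear, and it may rescue the by-visit tables. But Appendix A assigns results to visits, whereas threshold counts and listings are selected by period. Nothing in the visible text says the windows override SAP 8.2.

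A second point is that the public SAP is redacted. Section 8.3 is absent, the table header cites a note 5 that cannot be seen, and Appendix C uses a cumulative safety period that no visible section defines. Hidden text could bear on this. It would not remove the conflict between the visible 8.2 and Appendix A.

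Third, the values are not lost from the database. For children moving from placebo, the last value before Part 2 is the LUM/IVA baseline. Protocol 12.3.4 also asks for all safety data to be listed, and protocol 12.3.4.4 lists OE findings without a period limit. This stands as a limit on the consequence, and for OE the question is which listing shows the result. It does not restore the threshold counts. For children on LUM/IVA throughout, the Week 48 value does not serve as a baseline either.

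Fourth, the rule is the same in both arms, vital signs have no threshold criteria in Appendix D, and safety is descriptive without confidence intervals. All true. No directional bias is claimed; the problem is incomplete capture.

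**Conclusion.** The concern holds. As written, SAP 8.2 excludes same-day pre-dose Week 48 results from the Part 1 threshold counts and TE-period listings, SAP 8.4 does not recover them, and Appendix A sets the opposite boundary.

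The effect is confined to children who enter Part 2 and whose Week 48 assessments fall on the day of the first Part 2 dose. The documents do not say how many that will be, so the size can be given only per child, as upper limits on scheduled time points. The conclusion assumes that SAP 8.2 is applied literally by day, that SAP 8.4 is applied from the dose itself, and that no redacted text resolves the conflict. Under date-only programming the results are misattributed to Part 2 rather than dropped. No efficacy analysis is affected. The change should be made before the Part 1 data cut but does not threaten the trial's main conclusions.

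**What to change.** In SAP 8.2, for measured assessments in children entering Part 2, end the Part 1 TE period immediately before the first Part 2 dose, using date and time, to match Appendix A.

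State that scheduled Week 48 laboratory, vital-sign, OE and physical-examination results on that date with unknown time count as pre-dose Part 1 data. This extends Appendix A note 3, which covers only laboratory and vital-sign results. Exclude assessments scheduled after the dose: the 1-, 2- and 4-hour vital signs and the abbreviated physical examination.

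Keep adverse events with onset on that date in Part 2, as SAP 9.3.3.1 already defines them. Say so explicitly, because a pre-dose laboratory abnormality and an adverse event recorded on the same date could then sit in different parts.

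The cost is one or two sentences in SAP 8.2 and a datetime condition in the derivation. Data collection does not change.

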8.4 Part 2 Safety Period

The **Part 2 Safety Period** will include the time from the first dose of study drug of Part 2 until 14 days after the last dose of LUM/IVA or the completion of study participation, whichever occurs first.

Completion of study participation is defined as:

- For subjects who complete the study, the latest of the ETT Visit or Safety Follow-up Visit (if required).
- For subjects who prematurely discontinue study drug treatment during the study but do not withdraw consent (and assent, as applicable): the latest of ETT or Safety Follow-up Visit (if required).
- For subjects who withdraw consent or assent: date of withdrawal of consent or assent, whichever is earlier.

The Part 2 Safety Period will be used for analysis of safety data in the FA.

9 STATISTICAL ANALYSIS

9.1 General Considerations

As summarized in Table 7-1, the 2 treatment groups in Part 1 are

- LUM/IVA
- Placebo (PBO)

and the 2 treatment sequences from Part 1 to Part 2 are as follows:

- LUM/IVA → LUM/IVA
- PBO → LUM/IVA

Continuous variables will be summarized using the following descriptive summary statistics: the number of subjects (n), mean, SD, median, minimum value (min), and maximum value (max).

Categorical variables will be summarized using counts and percentages.

Unless otherwise specified,

- the **Study Baseline** value is defined as the most recent non-missing measurement (scheduled or unscheduled) collected before the first dose of study drug (including the matched placebo). The study baseline will be used to calculate the absolute and relative change from baseline for efficacy analyses, unless otherwise specified.
- the **LUM/IVA Baseline** value is defined as the most recent non-missing measurement (scheduled or unscheduled) collected before the first dose of study drug of Part 1 if the subject actually received at least one dose of LUM/IVA in Part 1, or before the first dose of study drug of Part 2 if the subject did not actually receive at least one dose of LUM/IVA in Part 1. The LUM/IVA baseline will be used to calculate the change from baseline in safety analysis in the FA, unless otherwise specified.

Absolute change from baseline will be calculated as post-baseline value – baseline value.

Relative change from baseline will be calculated as (post-baseline value – baseline value)/baseline value.

Unscheduled visits: Unscheduled visit measurements will be included in analysis as follows:

- 1) In scheduled visit windows per specified visit windowing rules
- 2) In the derivation of baseline and last on-treatment measurements
- 3) In the derivation of maximum and minimum values, and maximum and minimum change from baseline values during analysis period for safety analyses
- 4) In individual subject data listings as appropriate

Visit windowing rules: The analysis visit windows for protocol-defined visits are provided in [Appendix A](#).

Incomplete/missing data will not be imputed, unless specified otherwise.

Outliers: No formal statistical analyses will be performed to detect or remedy the presence of statistical outliers, unless specified otherwise.

9.2 Part 1 Analysis

The Part 1 analysis will be conducted after all subjects have completed the study Part 1 or have discontinued prematurely. The efficacy analysis and safety analysis will be based on the efficacy and safety data from study Part 1 only.

9.2.1 Background Characteristics

9.2.1.1 Subject Disposition

A disposition table will be provided for Part 1 with the number of subjects in:

- All Subjects Set

- Randomized
- Randomized but not dosed
- Full Analysis Set
- Safety Set

The number and percentage (based on the FAS) of subjects in each of the following disposition categories will be summarized by treatment group and overall:

- Completed Part 1 treatment
- Prematurely discontinued Part 1 treatment and the reason for discontinuation
- Completed Part 1 study participation
- Prematurely discontinued Part 1 study participation and the reason for discontinuation
- Continued to study Part 2

A listing will be provided for subjects who discontinued treatment or who discontinued study participation with reasons for discontinuation during Part 1.

9.2.1.2 Demographics and Baseline Characteristics

Demographics and baseline characteristics at study baseline will be summarized based on the FAS and presented by treatment group and overall.

Demographic data will include the following:

- Age at baseline (in years)
- Age group at baseline (<3 and ≥ 3 years)
- Sex (female and male)
- Ethnicity (Hispanic or Latino, not Hispanic or Latino, and not collected per local regulations)
- Race (White, Black or African American, Asian, American Indian or Alaska Native, Native Hawaiian or Other Pacific Islander, and not collected per local regulations)

[figure not shown]
Baseline characteristics will include the following:

- Weight (kg)
- Weight group (<14 kg and ≥ 14 kg)
- Weight-for-age z-score
- Stature (cm)
- Stature-for-age z-score
- BMI (kg/m^2)
- BMI-for-age z-score

Disease characteristics will include the following:

- $\text{LCI}_{2.5}$ at baseline

- 
- MRI global chest score at baseline
- 

In addition, data listings will also be provided for:

- Informed consent;
- Inclusion/Exclusion criteria violation for subjects with any such violations.

9.2.1.3 Medical History

Medical history will be coded by using the Medical Dictionary for Regulatory Activities (MedDRA). For the FAS, medical history will be summarized descriptively by system organ class (SOC) and preferred term (PT). The corresponding data listing will also be provided.

9.2.1.4 Prior and Concomitant Medications

Medications will be coded using the World Health Organization Drug Dictionary (WHO-DD) and categorized as follows:

Prior medication: any medication that was administered during the 28 days before the first dose of study drug (including the matched placebo) in the treatment period.

Concomitant medication during the Part 1 TE period: medication continued or newly received during the Part 1 TE period.

A given medication may be classified as follows: prior, concomitant, and both prior and concomitant.

If a medication has a completely missing or partially missing start/end date and it cannot be determined whether it was taken before the first dose date of study drug, concomitantly during the Part 1 TE period, or after the Part 1 TE period, it will be considered as prior and concomitant. Details for imputing missing or partial start and/or stop dates of medication are described in [Appendix B](#).

For FAS, prior medications and concomitant medications during the Part 1 TE period will be summarized descriptively by:

- 1) treatment group and overall, preferred name (PN)
- 2) treatment group and overall, anatomic class (ATC) level 1, ATC level 2, and PN

9.2.1.5 Study Drug Exposure

Study drug exposure summaries will be based on the Safety Set for the study Part 1 and presented by treatment group.

Duration of study drug exposure is defined as last dose date of Part 1 – first dose date of Part 1 + 1 day, regardless of any interruptions in dosing.

Duration of study drug exposure period (in weeks) will be summarized descriptively by the number of subjects (n), mean, SD, median, min, and max. It will also be summarized as a categorical variable by intervals using counts and percentages.

9.2.1.6 Study Drug Compliance

Percentage of study drug compliance during the study Part 1 will be summarized descriptively based on the FAS and will be presented by treatment group and overall.

Study drug compliance will be calculated as: $100 \times (1 - [\text{total number of days of study drug interrupted prior to the date of last dose in Part 1}] / [\text{duration of drug exposure in Part 1}])$. A study drug interruption on a given day is defined as an interruption of any study drug on that day. A study drug interruption that continues through the end of the study participation (i.e., subject does not resume study drug before the end of the study participation) will not be included in the compliance calculation.

Descriptive summary statistics include number of subjects (n), mean, SD, median, min, and max. It will also be summarized in categories: $<80\%$ and $\geq 80\%$ using frequency tables.

In addition, percentage of stick packs taken will be calculated using the following formula: $100 \times [(\text{total number of stick packs dispensed during Part 1}) - (\text{total number of stick packs returned during Part 1})] / (\text{total number of stick packs planned to be taken per day during Part 1} \times \text{duration of Part 1 drug exposure in days})$. Summary similar to those for the study drug compliance will be produced based on the FAS.

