### 9.1.3 Follow-up

Subjects will have a Safety Follow-up Visit 2 weeks ( $\pm$  4 days) after the last study drug dose. Safety Follow-up Visit assessments are listed in Table 3-2.

The Safety Follow-up Visit is required for 1) subjects who complete their Early Termination of Treatment (ETT) Visit <10 days after the last dose of study drug (Section 9.1.4) and 2) subjects who interrupt study drug treatment and complete their Week 96 Visit <10 days after the last dose of study drug; it is not required for subjects who continue onto commercially available, physician-prescribed LUM/IVA within 2 weeks ( $\pm$  4 days) of completing study drug treatment at the Week 96 or ETT Visit.

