#### 12.3.2.4 Study Drug Exposure and Compliance

Exposure to study drug (i.e., duration of treatment) will be summarized for the FAS in terms of duration of treatment a subject received (in days), defined as the last day minus the first day of study drug plus 1.

Dosing compliance will be summarized for the FAS and is calculated as the actual number of dosing occasions at which study drug was taken (including when administered at study visits), as a percentage of the planned number of dosing occasions.

Duration of treatment and dosing compliance will be summarized by means of descriptive summary statistics.

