9.2.1.7 Important Protocol Deviations

An important protocol deviation (IPD) is a deviation that may significantly affect the completeness, accuracy, or reliability of the study data or that may significantly affect a subject's rights, safety, or well-being. IPD rules will be developed and finalized before database cut/lock.

The protocol deviations that should be considered as potential IPDs include, but are not limited to:

- Subject was enrolled in the study despite the violation of inclusion/exclusion criteria
- Subject was less than 80% compliant with study drug for non-safety reasons
- Subject received prohibited concomitant medications
- Subject received the wrong treatment or incorrect doses
- Subject remained in the study despite meeting withdrawal criteria

Occurrence of any of these events should be considered as potential IPDs, but a blinded team should categorize them as IPDs only if they have the potential to significantly affect the completeness, accuracy, or reliability of the study data or that may significantly affect a subject's rights, safety, or well-being.

IPDs (from the clinical database or from the site deviation log) will be summarized descriptively based on the FAS and presented by treatment group and overall. Additionally, IPDs will be provided in an individual subject data listing.

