9.3.1.3 Study Drug Compliance

Percentage of study drug compliance during the study Part 2 will be summarized descriptively based on the FAS, Part 2 and presented by overall LUM/IVA treatment group.

[figure not shown]
Study drug compliance will be calculated as: $100 \times (1 - [\text{total number of days of LUM/IVA interrupted prior to the date of last dose of LUM/IVA in Part 2}] / [\text{duration of LUM/IVA exposure in Part 2}])$. A study drug interruption on a given day is defined as an interruption of any study drug on that day. A study drug interruption that continues through the end of the study participation (i.e., subject does not resume study drug before the end of the study participation) will not be included in the compliance calculation.

[figure not shown]
Descriptive summary statistics include the number of subjects (n), mean, SD, median, min, and max. It will also be summarized in categories: <80% and ≥80% using frequency tables. A listing containing subjects with study drug interruptions will be provided.

In addition, percentage of stick packs/tablets taken will be calculated using the following formula: $100 \times [(\text{total number of stick packs/tablets dispensed during Part 2}) - (\text{total number of stick packs/tablets returned during Part 2})] / (\text{total number of stick packs/tablets planned to be taken per day during Part 2} \times \text{duration of Part 2 drug exposure in days})$. Summary similar to those for the study drug compliance will be produced based on the FAS, Part 2.

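### The SAP's compliance measures end at the last dose taken in each part, so an interruption running up to the Week 48 or Week 96 Visit is left out, although the protocol divides by planned dosing occasions

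*SAP*

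**What the plan says.** Protocol 12.3.2.4 defines dosing compliance as the number of occasions on which drug was taken, expressed "as a percentage of the planned number of dosing occasions".

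SAP 9.2.1.6 defines it for Part 1 as 100 × (1 − interrupted days / exposure duration). Interrupted days are the "total number of days of study drug interrupted prior to the date of last dose in Part 1". SAP 9.2.1.5 defines exposure duration as "last dose date of Part 1 – first dose date of Part 1 + 1 day, regardless of any interruptions in dosing". A second measure, the percentage of stick packs taken, divides packs dispensed minus packs returned by the "total number of stick packs planned to be taken per day during Part 1" times that same duration.

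SAP 9.3.1.3 follows the same pattern for Part 2. It counts the "total number of days of LUM/IVA interrupted prior to the date of last dose of LUM/IVA in Part 2", and SAP 9.3.1.2 starts Part 2 exposure at the first Part 2 dose.

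Both compliance sections also exclude one kind of interruption: "A study drug interruption that continues through the end of the study participation", which the SAP explains as drug not being resumed before participation ends.

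The result is tabulated as <80% or ≥80%. SAP 9.2.1.7 lists, among potential important protocol deviations (IPDs), "Subject was less than 80% compliant with study drug for non-safety reasons".

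**The concern.** Off-drug days after the last dose of a part enter neither the numerator nor the denominator. The boundary between the parts makes this matter. Under Protocol Table 3-2, the dose given at the Week 48 Visit is the first open-label dose, so it cannot serve as the last Part 1 dose. If a child is off drug up to Week 48 and resumes there, the gap lies after the last Part 1 dose and before the first Part 2 dose, and neither part counts it. Yet the SAP's exclusion sentence, read plainly, covers only interruptions that are never resumed.

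The documents foresee such children. Protocol 11.5.3 provides for interruption with possible resumption. Protocol 9.1.3 makes a follow-up rule for "subjects who interrupt study drug treatment and complete their Week 96 Visit" within 10 days of the last dose; that limit decides who needs the follow-up visit and does not cap the length of an interruption.

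At stake is whether the compliance table and the <80% trigger show how much of the assigned treatment was taken. Protocol 12.3.3 keeps measurements made after treatment discontinuation in the efficacy analysis, so readers of the Week 48 MRI result will look to the compliance table for this. With 33 and 17 children planned per arm, one child is about 3% (1/33) or 6% (1/17) of an arm.

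**Working it through.** The documents give no numerical result for this point, so there is no stated figure to reproduce. The formulas are applied directly.

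**Inputs**
- Dosing every 12 hours, so 2 occasions a day (Protocol 9.1.2), at one stick pack per dose in Part 1 (Protocol Table 9-2).
- Week 48 target day 337 (SAP Table 12-1). Part 1 therefore has 336 planned days and 336 × 2 = 672 planned occasions.
- Week 48 may be delayed by up to 60 days after a pulmonary exacerbation (Protocol 9.1.2), giving 336 + 60 = 396 planned days.
- Assumptions: no interruption before the last dose, all unused packs returned, and planned occasions running to the Week 48 Visit.

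**Formulas**, with L the day of the last Part 1 dose
- SAP, days: 100 × (1 − 0/L)
- SAP, packs: 100 × 2L/(2 × L)
- Protocol: 100 × 2L/672

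| Last Part 1 dose | End-of-part gap (days) | SAP, days | SAP, packs | Protocol |
|---|---|---|---|---|
| Day 84 | 252 | 100% | 100% | 168/672 = 25.0% |
| Day 200 | 136 | 100% | 100% | 400/672 = 59.5% |
| Day 252 | 84 | 100% | 100% | 504/672 = 75.0% |
| Day 268 | 68 | 100% | 100% | 536/672 = 79.8% |
| Day 269 | 67 | 100% | 100% | 538/672 = 80.1% |
| Day 300 | 36 | 100% | 100% | 600/672 = 89.3% |

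**Where the gap falls.** Move the 84-day gap to mid-period, with dosing resumed to Day 336. The SAP day measure gives 100 × (1 − 84/336) = 75.0%, the pack measure 504/672 = 75.0% and the protocol 75.0%. For the same drug taken, the SAP reports 75% or 100% according to timing.

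**80% threshold.** 0.20 × 336 = 67.2, so gaps of 68 days or more are below 80% on the protocol denominator. With the 60-day delay, 0.20 × 396 = 79.2, so the threshold is 80 days or more.

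**With an earlier interruption.** For a last dose on Day 252 and 20 interrupted days before it, the SAP day measure gives 100 × (1 − 20/252) = 92.1%. The protocol gives 2 × 232/672 = 69.0%. The SAP value is no longer 100%, but the end gap is still missing.

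**Part 2.** The formulas have the same form over that part's own 336 days. An interruption still open at Week 96 is omitted both by the formula and by the exclusion sentence.

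**The case against.** - *The protocol comparison is one reading.* Protocol 12.3.2.4 does not say when planned occasions end. If they end at permanent discontinuation, both definitions give 100% for a child who stops for good on Day 200 with no earlier gap. This stands. A reader might infer that every early stopper is misreported against the protocol, but the documents do not support that. The divergence is clear only for children who have not permanently discontinued.
- *The figures are conditional.* This stands. A reader might infer that every long end gap lands in the ≥80% category. It need not: with a last dose on Day 200 and 45 earlier interrupted days, the SAP gives 1 − 45/200 = 77.5%, which is flagged.
- *The shortfall appears elsewhere.* Largely true. Exposure duration is summarised with its minimum and by intervals (200/7 = about 29 weeks for a Day 200 last dose). Disposition tables cover discontinuation, adverse events leading to interruption are tabulated, and SAP 9.3.1.3 promises a Part 2 listing of interruptions. However, disposition does not identify a child who only interrupted, and SAP 9.2.1.6 promises no matching Part 1 listing.
- *The exclusion is declared.* It is, in both parts. One could read it as referring to Part 1 participation, which SAP 8.2 ends the day before the first Part 2 dose. The sentence does not name Part 1, and on that reading the departure from the protocol would remain.
- *The deviation consequence is limited.* This stands. The listed deviations are only potential and not exhaustive, a blinded team adjudicates them, and the trigger covers non-safety reasons. A liver-test interruption is outside it under either formula.
- *No result changes.* Correct. A reader might infer that the Week 48 MRI comparison is biased, but no efficacy estimate uses compliance and the Full Analysis Set has no compliance condition.

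**Conclusion.** The concern holds for a narrow but foreseeable group: children who have not permanently discontinued and are off drug up to the Week 48 or Week 96 Visit. For them the SAP omits the end-of-part gap from both measures, departs from Protocol 12.3.2.4 without explanation, and loses a gap before Week 48 in both parts even when dosing resumes.

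The contrast of 100% with 59.5% for a last dose on Day 200, and the 68-day threshold, rest on four conditions: no earlier interruption, unused packs returned, Week 48 on Day 337, and planned occasions running to the visit. With a 60-day delay the threshold is 80 days. For permanent discontinuers the two definitions may agree, and early stopping still shows in the exposure and disposition tables.

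The effect is confined to the compliance tables and the <80% potential-deviation trigger. This is a minor correction worth making.

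**What to change.** Align SAP 9.2.1.6 and 9.3.1.3 with Protocol 12.3.2.4, and state when planned dosing ends for analysis purposes.

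- Children not permanently discontinued: run the denominator of both measures to the day before the first Part 2 dose (Part 1) or to the Week 96 Visit (Part 2), and count the end-of-part gap as interrupted.
- Permanent discontinuers: stop the denominator at the discontinuation date.
- Reword the exclusion sentence to match, and base the <80% category and the potential-deviation trigger on the new figure.

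For the Day 200 example with dosing resumed at Week 48, the revised day measure is 100 × (1 − 136/336) = 59.5% and the pack measure is 400/(2 × 336) = 59.5%, both equal to the protocol value.

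The cost is one changed derivation and slightly lower reported compliance. No new visit is needed.
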